As a CYP3A4 inducer, dabrafenib, when administered 150 mg BID in combination with midazolam (a substrate of CYP3A4), significantly reduced the midazolam exposure by 74% (the ratios of midazolam with or without dabrafenib were 0.39 for C_{max} and 0.26 for AUC). Dabrafenib thus induces CYP3A4 metabolism and may induce other enzymes such as CYP2B6, CYP2C8, CYP2C9, and CYP2C19. Co-administration of dabrafenib and medicinal products which are affected by the induction of these enzymes such as hormonal contraceptives, warfarin, or dexamethasone may result in decreased concentrations and loss of efficacy.

Based on preclinical in vitro studies, dabrafenib was shown to be primarily metabolized by CYP2C8 and CYP3A4. Co-administration of ketoconazole (CYP3A4 inhibitor) increased the AUC of dabrafenib by 57%. Medicinal products that are strong inhibitors or inducers of CYP2C8 or CYP3A are likely to increase or decrease, respectively, dabrafenib concentrations. Alternative agents should be considered during administration with dabrafenib when possible. Use caution if strong inhibitors (e.g., ketoconazole, nefazodone, clarithromycin, ritonavir) or inducers (e.g., rifampin, phenytoin, carbamazepine, phenobarbital) of CYP2C8 or CYP3A4 are coadministered with dabrafenib.

Pharmacodynamic effect of dabrafenib:

Median tumor pERK inhibition was 83.9% (range: 38.0 to 93.3%) in BRAF mutant melanoma subjects receiving doses of 70 to 200 mg BID. The relationship between exposure and % pERK inhibition was characterized using a maximum response (E_{max}) model with 100% maximum inhibition and IC_{50} of 134 ng/mL (95% CI: 92.7, 155) based on the sum of the potency-adjusted parent and active metabolite concentrations. A dose-related decrease in pERK was predicted with total daily doses <200 mg (100 mg BID) dabrafenib, with a plateau occurring beyond total daily doses of 200 mg thereafter.

Selection of the RP2D:

The single-agent MTD for dabrafenib was not reached. A dose of 150 mg BID was selected for further single-agent development, based on the following PK/pharmacodynamics, safety, and activity: a) dose increases beyond 150 mg BID yielded no increase in C_{max} and <50% increase in AUC; b) incidence and severity of AEs was similar at 100-300 mg BID; c) pERK target suppression was >80%; and d) the tumor response rate (RR) was 50% at 150 mg BID.

CONFIDENTIAL

This document is confidential. Do not disclose or use except as authorized.

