5.4.3 Concomitant Medications to be used with caution

The following therapies are to be used with caution during the Screening and Treatment Phase (including retreatment for post-complete response relapse) of this trial:

- Mild or moderate inhibitors/inducers of CYP 3A4, 2C8, Pgp, and Bcrp should be used with caution as dabrafenib serum concentrations may be altered. Because the lists of these agents are constantly changing, it is important to regularly consult a frequently-updated list such as <http://medicine.iupui.edu/clinpharm/ddis/table.aspx>; medical reference texts such as the Physicians' Desk Reference may also provide this information.
- Dabrafenib may induce CYP 3A4, 2B6, and possibly 2C8/9 and 2C19. Use concomitant medications that are substrates of these isoenzymes with caution as there may be loss of efficacy. Substitute with other medications that are not affected if possible.
- Because there is a low potential for interaction of trametinib with other concomitantly administered drugs through the cytochrome P450 system, the Principal Investigator should be alerted if the patient is taking any agent known to affect or with the potential to affect selected CYP450 isoenzymes.

5.4.4 Alerting the Principal Investigator about specific agents and capturing the concurrent use of all drugs, over-the-counter medications, or alternative therapies in the case report form

- Because there is a potential for interaction of dabrafenib with other concomitantly administered drugs through the cytochrome P450 system, the case report form must capture the concurrent use of all other drugs, over-the-counter medications, or alternative therapies. The Principal Investigator must be alerted if the patient is taking any agent known to affect or with the potential to affect selected CYP450 isoenzymes.
- Because there is a low potential for interaction of trametinib with other concomitantly administered drugs through the cytochrome P450 system, the case report form must capture the concurrent use of all other drugs, over-the-counter medications, or alternative therapies. The Principal Investigator should be alerted if the patient is taking any agent known to affect or with the potential to affect selected CYP450 isoenzymes.

CONFIDENTIAL

This document is confidential. Do not disclose or use except as authorized.

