5.8 Contraception

Pembrolizumab may have adverse effects on a fetus in utero. Furthermore, it is not known if pembrolizumab has transient adverse effects on the composition of sperm. For this trial, male subjects will be considered to be of non-reproductive potential if they have azoospermia (whether due to having had a vasectomy or due to an underlying medical condition).

Female subjects will be considered of non-reproductive potential if they are either:

(1) Postmenopausal (defined as at least 12 months with no menses without an alternative medical cause; in women < 45 years of age a high follicle stimulating hormone (FSH) level in the postmenopausal range may be used to confirm a post-menopausal state in women not using hormonal contraception or hormonal replacement therapy. In the absence of 12 months of amenorrhea, a single FSH measurement is insufficient.);

OR

(2) Have had a hysterectomy and/or bilateral oophorectomy, bilateral salpingectomy or bilateral tubal ligation/occlusion, at least 6 weeks prior to screening;

OR

CONFIDENTIAL

This document is confidential. Do not disclose or use except as authorized.

(3) Has a congenital or acquired condition that prevents childbearing. Female and male subjects of reproductive potential must agree to avoid becoming pregnant or impregnating a partner, respectively, while receiving study drug and for 120 days after the last dose of study drug by complying with one of the following:

Female subjects of childbearing potential and male subjects with partners of childbearing potential must:

(1) Practice abstinence† from heterosexual activity;

OR

(2) Use (or have their partner use) acceptable contraception during heterosexual activity.

Acceptable methods of contraception are:

Single method (one of the following is acceptable):

- Intrauterine device (IUD)
- Vasectomy of a female subject's male partner
- Contraceptive rod implanted into the skin

Combination method (requires use of two of the following):

- Diaphragm with spermicide (cannot be used in conjunction with cervical cap/spermicide)
- Cervical cap with spermicide (nulliparous women only)
- Contraceptive sponge (nulliparous women only)
- Male condom or female condom (cannot be used together)
- Hormonal contraceptive: oral contraceptive pill (estrogen/progestin pill or progestin-only pill), contraceptive skin patch, vaginal contraceptive ring, or subcutaneous contraceptive injection

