†Abstinence (relative to heterosexual activity) can be used as the sole method of contraception if it is consistently employed as the subject's preferred and usual lifestyle and if considered acceptable by local regulatory agencies and ERCs/IRBs. Periodic abstinence (e.g., calendar, ovulation, sympto-thermal, post-ovulation methods, etc.) and withdrawal are not acceptable methods of contraception.

‡If a contraceptive method listed above is restricted by local regulations/guidelines, then it does not qualify as an acceptable method of contraception for subjects participating at sites in this country/region.

Subjects should be informed that taking the study medication may involve

CONFIDENTIAL

This document is confidential. Do not disclose or use except as authorized.

unknown risks to the fetus (unborn baby) if pregnancy were to occur during the study. In order to participate in the study subjects of childbearing potential must adhere to the contraception requirement (described above) from the day of study medication initiation (or 14 days prior to the initiation of study medication for oral contraception) throughout the study period up to 120 days after the last dose of trial therapy. If there is any question that a subject of childbearing potential will not reliably comply with the requirements for contraception, that subject should not be entered into the study.

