8.2 Dabrafenib mesylate (GSK2118436B) (NSC 763760)

8.2.1 **Chemical Name:** N-{3-[5-(2-Amino-4-pyrimidinyl)-2-(1,1-dimethylethyl)-1,3-thiazol-4-yl]-2-fluorophenyl}-2,6-difluorobenzene sulfonamide, methanesulfonate salt

8.2.2 **Other Names:** GSK2118436, GSK2118436A (free base), Tafinlar

8.2.3 **Classification:** BRAF inhibitor

8.2.4 **CAS Registry Number:** 1195768-06-9

8.2.5 **Molecular Formula:** $C_{23}H_{20}F_3N_5O_2S_2 \cdot CH_4O_3S$

8.2.6 **M.W.:** 615.68 (mesylate salt)

8.2.7 **Mode of Action:** Dabrafenib mesylate (GSK2118436B) is a potent and selective BRAF kinase inhibitor. This inhibition suppresses downstream activity of pERK, a biomarker, and has antiproliferative activity against BRAF mutant tumors. The mode of action is consistent with ATP-competitive inhibition.

8.2.8 **How Supplied:** Dabrafenib mesylate (GSK2118436B) capsules will be supplied commercially.

- 50 mg capsule is Swedish orange, size 2 with markings of four black bars.
- 75 mg capsule is pink, size 1 with markings of four black bars.

Capsule excipients include microcrystalline cellulose, magnesium stearate (vegetable source), colloidal silicon dioxide. Shell composition consists of an opaque hypromellose capsule, composed of red iron oxide (E172), titanium dioxide (E171), and hypromellose (E464). Four black bars are printed on the hypromellose capsules using black ink. The black ink contains black iron oxide (E172), shellac, propylene glycol, and ammonium hydroxide.

CONFIDENTIAL

This document is confidential. Do not disclose or use except as authorized.

8.2.9 **Storage:** Store between 15°C to 30°C (59°F to 86°F).

8.2.10 **Stability:** Shelf-life studies of dabrafenib mesylate (GSK2118436B) are ongoing.

8.2.11 **Route of Administration:** Oral administration. Take dabrafenib mesylate (GSK2118436B) 1 hour prior or 2 hours after a meal. If a dose is missed, it should not be taken if it is less than 6 hours until the next dose.

8.2.12 **Potential Drug Interactions:** *In vitro* studies show that dabrafenib mesylate (GSK2118436B) induces CYP3A4, 2B6, 2C9,8, 2C9, and 2C19 enzymes. Use caution in patients who are taking substrates that are metabolized in these enzyme pathways.

Dabrafenib mesylate (GSK2118436B) metabolism appears to be mediated by CYP3A4 and CYP2C8. Use caution if strong inducers or inhibitors of CYP2C8 or 3A4 are co-administered with dabrafenib.

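### Section 5.8 lets a hormonal contraceptive count as one of two required methods for women taking dabrafenib, although Section 2.2.2.2 says dabrafenib may make it less effective

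*Combined protocol and SAP*

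**What the plan says.** Section 5.8 gives participants of reproductive potential three ways to comply: abstinence, one method from a short list, or two methods from a longer list.

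- The short list is headed "Single method (one of the following is acceptable" and holds an IUD, vasectomy of the partner, and a contraceptive rod under the skin.
- The longer list is headed "Combination method (requires use of two of the following" and holds diaphragm, cervical cap, sponge, condom and, last, "Hormonal contraceptive: oral contraceptive pill (estrogen/progestin pill or progestin-only pill), contraceptive skin patch, vaginal contraceptive ring, or subcutaneous contraceptive injection".

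The section speaks of pembrolizumab and of study drug in general. It does not mention dabrafenib or separate the cohorts. It does plan for pill users, since the requirement runs from the first day of study medication "or 14 days prior to the initiation of study medication for oral contraception".

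Section 2.2.2.2 describes dabrafenib as an inducer of CYP3A4 and possibly of other enzymes. It says that giving it with products affected by that induction, "such as hormonal contraceptives, warfarin, or dexamethasone may result in decreased concentrations and loss of efficacy".

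Two other places give general advice. Section 5.4.3 asks for caution with substrates of the induced enzymes and adds: "Substitute with other medications that are not affected if possible". Section 8.2.12 says: "Use caution in patients who are taking substrates that are metabolized in these enzyme pathways". Neither mentions contraception.

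Sections 3.1.9 and 3.2.10 class both dabrafenib and trametinib as drugs that may harm a fetus or end a pregnancy.

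**The concern.** The section that decides whether a woman's contraception is adequate accepts a method that the protocol's own pharmacology section says may fail with one of the study drugs. Section 3.1.9 refers to 5.8, and 5.8 makes adherence a condition of taking part, so a site checking contraception will read 5.8. A cohort 1 woman using the pill and a condom meets both 3.1.9 and 5.8.

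Section 5.8 asks for two methods from the longer list because it does not accept any of them alone. If one of the two is weakened, she has less protection than the rule was written to secure, while taking two drugs with teratogenic potential. What is at stake is participant safety, not the efficacy analysis.

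**Working it through.** The plan states no figure to reproduce. The check sets the sections side by side and counts what 5.8 permits.

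**1. Who is affected.** Section 2.3 gives dabrafenib to cohort 1 only; cohort 2 receives trametinib. Section 8.3.14 does not anticipate interactions between trametinib and sensitive CYP3A4 substrates. Female partners of male participants do not take dabrafenib. The point therefore concerns female cohort 1 participants of childbearing potential. The cohort plans 25 patients in all (Section 13.2); the number of such women is not given.

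**2. For how long.** The lead-in is 2 weeks and the combined phase is two 3-week cycles: 2 + 2 × 3 = 8 scheduled weeks of dabrafenib. Two routes can extend this:
- Targeted therapy may be resumed on progression (Section 10, footnote a).
- Dabrafenib may continue if trametinib and pembrolizumab both stop for toxicity (Section 6.2).

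**3. What 5.8 permits.** The longer list has five entries, counting male or female condom as one. All pairs: 5 × 4 / 2 = 10. Diaphragm with cap is ruled out, leaving 9. The cap and sponge are limited to nulliparous women, so other women have three entries and 3 × 2 / 2 = 3 pairs.

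| | Pairs allowed | With a hormonal method | Without |
|---|---|---|---|
| Nulliparous | 9 | 4 | 5 |
| Not nulliparous | 3 | 2 | 1 (diaphragm and condom) |

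These count entries in a list. They do not show how many women use each method.

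**4. Size of the interaction.** No figure is given for contraceptives. The only measured figure given for a CYP3A4 substrate is that dabrafenib at 150 mg twice daily, the trial dose, "significantly reduced the midazolam exposure by 74" per cent (AUC ratio 0.26; 1 − 0.26 = 0.74). It shows that induction at this dose is not trivial. It does not measure loss of contraceptive effect.

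**5. Whether another section closes the gap.**
- Sections 5.4.3 and 8.2.12 advise caution but do not alter the list in 5.8.
- Section 5.4.4 asks for concomitant drugs to be recorded, and for the principal investigator to be alerted to drugs that affect CYP450 enzymes. A contraceptive that dabrafenib affects is the reverse case.
- Section 5.2 schedules pregnancy tests, which detect a pregnancy but do not prevent one.

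**The case against.** The strongest reply is that the protocol already deals with this. Section 5.4.3 is an operative section. Read with 2.2.2.2, its advice to use affected substrates with caution and to substitute where possible reaches a hormonal contraceptive. Section 5.8 never accepts a pill, patch, ring or injection alone, so a second method is always in place. Scheduled exposure is short and confined to one cohort. Much of this stands, and it keeps the point modest. It does not remove it, because advisory text elsewhere leaves the method listed as acceptable in the section that sites apply.

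A reader might infer several stronger things that the documents do not support:

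- *That the woman is left with a barrier method alone.* Section 2.2.2.2 says concentrations and efficacy may fall. It does not say the effect is lost in every woman.
- *That women are not warned.* Appendix B, on possible drug interactions, and the consent form could not be checked. The claim is only that 5.8 lacks the exception.
- *That contraceptive exposure falls by 74 per cent.* That figure is for midazolam.
- *That the two-method wording of 3.1.9 is a safety gap because 5.8 accepts some methods alone.* Section 3.1.9 is the stricter text, and read literally it leads to no unsafe outcome. Aligning it with 5.8 would remove a second method from, for example, a woman relying on an implanted rod.

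**Conclusion.** The inconsistency is real and worth correcting. Section 5.8 accepts, for women taking dabrafenib, a method that 2.2.2.2 says may lose efficacy, and no section available for review changes what 5.8 accepts. A compliant cohort 1 woman may have less protection than 5.8 intends during the 8 scheduled weeks and any later continuation or resumption. How much less, and for how many women, cannot be stated from the documents. No endpoint, power figure or estimate is affected.

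The conclusion rests on two assumptions. The first is that sites treat 5.8 as the working rule, as 3.1.9 directs. The second is that Appendix B, whatever it says, does not amend 5.8. A warning there would reduce the practical risk, but the listing in 5.8 would still need correcting.

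**What to change.** Add to Section 5.8:

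> Cohort 1 women: while taking dabrafenib (including any continuation or resumption), and until enzyme induction has worn off, hormonal methods do not count toward this requirement. This includes the implanted rod and a hormonal IUD unless the sponsor confirms that they are unaffected. Use abstinence, a non-hormonal single method, or two non-hormonal methods from the combination list. See 2.2.2.2 and 5.4.3.

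The sponsor should state the period after the last dabrafenib dose. The documents do not say how long induction lasts, so none can be derived here. The 120 days that 5.8 already uses after the last dose of study drug, counted from the last dabrafenib dose, would be a conservative default. The sponsor also needs to settle the status of the rod and the IUD, because 5.8 does not say whether either is hormonal. Leave the two-method wording in 3.1.9 unchanged.

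The cost is fewer options for cohort 1 women in that period. Counting three single methods, the pairs and abstinence, 5.8 now offers 3 + 9 + 1 = 13 options to a nulliparous woman and 3 + 3 + 1 = 7 to others. With the hormonal pairs and the rod excluded, 13 − 4 − 1 = 8 and 7 − 2 − 1 = 4 remain. If the IUD is excluded as well, 7 and 3 remain. These counts apply 5.8 alone; 3.1.9 read literally still asks for two methods. No woman is left without a compliant choice, and treatment, visits and analysis are unchanged.

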6. DOSING DELAYS/DOSE MODIFICATION CRITERIA

Dose delays and modifications must be made using the following criteria. Toxicity assessments will be done using the CTEP Active Version of the NCI Common Terminology Criteria for Adverse Events (CTCAE) which is identified and located on the CTEP website at:
http://ctep.cancer.gov/protocolDevelopment/electronic_applications/ctc.htm.

If possible, symptoms should be managed symptomatically. In the case of toxicity, appropriate medical treatment should be used (including anti-emetics, anti-diarrheals, etc.).

6.1 Pembrolizumab Dose Modifications

Pembrolizumab will be withheld for drug-related Grade 4 hematologic toxicities, non- hematological toxicity \geq Grade 3 including clinically significant laboratory abnormalities despite appropriate replacement therapies when appropriate, and severe or life-threatening AEs as per Table 6.1.

Table 6.1 Pembrolizumab dose modification requirements for drug-related adverse events

Toxicity	Hold Treatment For Grade	Timing for Restarting Treatment	Discontinue Subject
Diarrhea/Colitis	2-3	Toxicity resolves to Grade 0-1.	Toxicity does not resolve within 12 weeks of last dose or inability to reduce corticosteroid to 10 mg or less of prednisone or equivalent per day within 12 weeks.
	4	Permanently discontinue	Permanently discontinue
AST, ALT, or Increased Bilirubin	2	Toxicity resolves to Grade 0-1	Toxicity does not resolve within 12 weeks of last dose.
	3-4	Permanently discontinue (see exception below) ¹	Permanently discontinue
Type 1 Diabetes Mellitus (if new onset) or Hyperglycemia	T1DM or 3-4	Hold pembrolizumab for new onset Type 1 diabetes mellitus or Grade 3-4 hyperglycemia associated with evidence of beta cell failure.	Resume pembrolizumab when patients are clinically and metabolically stable.
Hypophysitis	2-3	Toxicity resolves to Grade 0-1	Toxicity does not resolve within 12 weeks of last dose or inability to reduce corticosteroid to 10 mg or less of

CONFIDENTIAL

This document is confidential. Do not disclose or use except as authorized.

Toxicity	Hold Treatment For Grade	Timing for Restarting Treatment	Discontinue Subject
			prednisone or equivalent per day within 12 weeks.
	4	Permanently discontinue	Permanently discontinue
Hyperthyroidism	3	Toxicity resolves to Grade 0-1	Toxicity does not resolve within 12 weeks of last dose or inability to reduce corticosteroid to 10 mg or less of prednisone or equivalent per day within 12 weeks.
	4	Permanently discontinue	Permanently discontinue
Hypothyroidism	2-4	Therapy with pembrolizumab can be continued while treatment for the thyroid disorder is instituted	Therapy with pembrolizumab can be continued while treatment for the thyroid disorder is instituted.
Infusion Reaction	3-4	Permanently discontinue	Permanently discontinue
Pneumonitis	2	Toxicity resolves to Grade 0-1	Toxicity does not resolve within 12 weeks of last dose or inability to reduce corticosteroid to 10 mg or less of prednisone or equivalent per day within 12 weeks.
	3-4	Permanently discontinue	Permanently discontinue
Renal Failure or Nephritis	2	Toxicity resolves to Grade 0-1	Toxicity does not resolve within 12 weeks of last dose or inability to reduce corticosteroid to 10 mg or less of prednisone or equivalent per day within 12 weeks.
	3-4	Permanently discontinue	Permanently discontinue
Hematologic Toxicity	4	Toxicity resolves to Grade 0-1 or baseline	Toxicity does not resolve within 12 weeks of last infusion. Permanent discontinuation should be considered for any severe or life-threatening event.
All Other Drug-Related Toxicity ^{2,3}	3 or Severe	Toxicity resolves to Grade 0-1	Toxicity does not resolve within 12 weeks of last dose or inability to reduce corticosteroid to 10 mg or less of prednisone or equivalent per day within 12 weeks.
	4	Permanently discontinue	Permanently discontinue
Note: Permanently discontinue for any severe or Grade 3 drug-related AE that recurs or any life-threatening event.			
¹ For patients with liver metastasis who begin treatment with Grade 2 AST or ALT, if AST or ALT increases by greater than or equal to 50% relative to baseline and lasts for at least 1 week then patients should be discontinued.			
² Patients with intolerable or persistent Grade 2 drug-related AE may hold study medication at physician discretion. Permanently discontinue study drug for persistent Grade 2 adverse reactions for which treatment with study drug has been held, that do not recover to Grade 0-1 within 12 weeks of the last dose.			
³ Exception to be treated similar to grade 1 toxicity: Grade 2 alopecia, grade 2 fatigue			

6.1.1 Dosing interruptions are permitted in the case of medical / surgical events or logistical reasons not related to study therapy (e.g., elective surgery, unrelated medical events, patient vacation, and/or holidays). In these cases only, subjects must be placed back on study therapy within 2 weeks of the scheduled interruption, unless otherwise discussed with the PI of the study. The reason for interruption must be documented in the patient's study record.

CONFIDENTIAL

This document is confidential. Do not disclose or use except as authorized.

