Grade 2 Requires infusion interruption but responds promptly to symptomatic treatment (e.g., antihistamines, NSAIDs, narcotics, IV fluids); prophylactic medications indicated for < =24 hrs	Stop infusion and monitor symptoms. Additional appropriate medical therapy may include but is not limited to: IV fluids Antihistamines NSAIDs Acetaminophen Narcotics Increase monitoring of vital signs as medically indicated until the subject is deemed medically stable in the opinion of the investigator. If symptoms resolve within one hour of stopping drug infusion, the infusion may be restarted at 50% of the original infusion rate (e.g., from 100 mL/hr to 50 mL/hr). Otherwise dosing will be held until symptoms resolve and the subject should be premedicated for the next scheduled dose. Subjects who develop Grade 2 toxicity despite adequate premedication should be permanently discontinued from further trial treatment administration.	Subject may be premedicated 1.5h (± 30 minutes) prior to infusion of pembrolizumab (MK-3475) with: Diphenhydramine 50 mg po (or equivalent dose of antihistamine). Acetaminophen 500-1000 mg po (or equivalent dose of antipyretic).
Grades 3 or 4 Grade 3: Prolonged (i.e., not rapidly responsive to symptomatic medication and/or brief interruption of infusion); recurrence of symptoms following initial improvement; hospitalization indicated for other clinical sequelae (e.g., renal impairment, pulmonary infiltrates) Grade 4: Life-threatening; pressor or ventilatory support indicated	Stop Infusion. Additional appropriate medical therapy may include but is not limited to: IV fluids Antihistamines NSAIDs Acetaminophen Narcotics Oxygen Pressors Corticosteroids Epinephrine Increase monitoring of vital signs as medically indicated until the subject is deemed medically stable in the opinion of the investigator. Hospitalization may be indicated. Subject is permanently discontinued from further trial treatment administration.	No subsequent dosing
Appropriate resuscitation equipment should be available in the room and a physician readily available during the period of drug administration.		

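### The note under Table 6.1 requires permanent pembrolizumab discontinuation in situations where three of the table's own rows allow restart or continuation, and no precedence is stated

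*Combined protocol and SAP*

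**What the plan says.** The opening of Section 6 makes its dose-delay and modification criteria mandatory, and the title of Table 6.1 calls its contents requirements. The note closing the table is: "Note: Permanently discontinue for any severe or Grade 3 drug-related AE that recurs or any life-threatening event". It has two limbs, one for recurrence and one for life-threatening events, and neither names an exempt row.

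Three rows of the same table bear on it:

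- **Hematologic toxicity, Grade 4.** Treatment is held, and the restart condition is "Toxicity resolves to Grade 0-1 or baseline". The subject is discontinued if the toxicity has not resolved within 12 weeks. The row then adds: "Permanent discontinuation should be considered for any severe or life-threatening event".
- **Type 1 diabetes or hyperglycemia, Grade 3-4.** The restart column says "Hold pembrolizumab for new onset Type 1 diabetes mellitus or Grade 3-4 hyperglycemia associated with evidence of beta cell failure". The discontinuation column says "Resume pembrolizumab when patients are clinically and metabolically stable", and the row contains no stopping criterion.
- **Hypothyroidism, Grade 2-4.** Both the restart and the discontinuation columns say "Therapy with pembrolizumab can be continued while treatment for the thyroid disorder is instituted".

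The opening sentence of Section 6.1 has pembrolizumab withheld for drug-related Grade 4 hematologic toxicity, for non-hematological toxicity of Grade 3 or more, "and severe or life-threatening AEs as per Table 6.1". Section 7.1, among the criteria for a serious adverse event, defines life-threatening as the investigator's view that the patient is at immediate risk of death.

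**The concern.** A site treating a patient with one of these events has two binding instructions and no rule for choosing between them. One site may stop pembrolizumab for good and another may restart or continue it. Each could show that it followed the table, and each could be cited for deviating from it. The matter at stake is re-exposure after serious toxicity in a study that combines pembrolizumab with one or two targeted agents. Pembrolizumab exposure and the number of patients stopped for toxicity would also partly reflect how each site read the table.

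**Working it through.** No arithmetic applies. The check sets each row against the note and asks when both apply to the same event.

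**Step 1: which rows can conflict at Grade 4.** Table 6.1 has eleven toxicity rows. Four stop permanently at Grade 4: diarrhea/colitis, hypophysitis, hyperthyroidism and all other drug-related toxicity. Four stop at Grade 3-4: hepatic (with an exception in footnote 1), infusion reaction, pneumonitis and renal. That makes 4 + 4 = 8 rows that agree with the note at Grade 4, subject to the hepatic exception. The remaining 11 - 8 = 3 do not stop at Grade 4.

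**Step 2: row against note for those three.**

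| Row | What the row directs | What the note directs | When both apply |
|---|---|---|---|
| Hematologic, Grade 4 | Restart on recovery; permanent stop is discretionary for a life-threatening event | Permanent stop | Any life-threatening hematologic event |
| Type 1 diabetes / hyperglycemia, Grade 3-4 | Hold, then resume when stable | Permanent stop | Event judged life-threatening, or a Grade 3 event that recurs |
| Hypothyroidism, Grade 2-4 | Continue | Permanent stop | Event judged life-threatening, or a Grade 3 event that recurs |

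**Step 3: how much each conflict assumes.** The hematologic conflict assumes nothing. Row and note name the same trigger, a life-threatening event; one leaves the decision open and the other makes it. The other two need a fact about the event: either the investigator judges it life-threatening in the Section 7.1 sense, or it is a drug-related Grade 3 event that has recurred. Both rows cover Grades 3 and 4 and carve out neither case.

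**Step 4: is there a precedence rule?** Section 6.1 contains none. Where the table intends an exception it marks one: footnote 1 for hepatic events, and footnote 3 for Grade 2 alopecia and fatigue. No exception is marked for these three rows.

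**The case against.** The best defense is that row and note are meant to work together. The row governs the ordinary event, and the note adds a limit for recurrence or immediate danger to life. This works well for a row such as diarrhea/colitis, where Grade 3 is held and restarted and the note then deals with recurrence. It does not rescue the hematologic row, which addresses the life-threatening case itself and answers it differently. It is weaker for the other two rows as well, because their discontinuation column is filled with an instruction to resume or continue. The opposite defense, that a specific row overrides a general note, is equally possible, and neither is written down.

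A reader might infer three stronger points that the documents do not support.

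- **That every Grade 4 event in these rows is caught.** The note is triggered by a life-threatening event, not by a grade. Table 5.4 does say "Grade 4: Life-threatening; pressor or ventilatory support indicated", but only for infusion reactions. Section 7.1 makes the term an investigator's judgement, and the opening of Section 6.1 lists Grade 4 hematologic toxicity separately from life-threatening events. A Grade 4 event without immediate risk of death, and outside the recurrence limb, can simply follow its row.
- **That the opening sentence of Section 6.1 flatly contradicts the hypothyroidism row.** The sentence refers to Table 6.1 and mentions replacement therapy, so it can be read as deferring to the table. It is unclear and should be aligned, but it is not a clear separate contradiction.
- **That the conflict enters the stage 2 decision.** The design narratives in the synopsis and in Sections 1.1 and 5.1 speak of patients remaining on pembrolizumab, but they send the reader to the statistical section. There, Section 13.1 counts CR, PR or SD at the week-24 scan while off targeted therapy, with no requirement of ongoing pembrolizumab. Section 13.7.2 adds that incorrect drug administration does not exclude a patient from the response analysis. Stopping or continuing pembrolizumab therefore does not by itself reclassify anyone.

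**Conclusion.** The contradiction is real and limited. It is explicit for life-threatening hematologic events. For type 1 diabetes/hyperglycemia and hypothyroidism it is conditional on an event judged life-threatening or on a recurrent Grade 3 event. Three of eleven rows are involved. No sample size, error rate, stopping boundary or endpoint definition changes.

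The number of patients affected cannot be estimated. Section 2.2.1.5 gives hypothyroidism in 8.3% of patients on single-agent pembrolizumab without a split by grade, and the two hypothyroid cases in the triplet results of Section 2.2.1.2 were both Grade 1. The documents give no frequency for Grade 4 hematologic toxicity or Grade 3-4 hyperglycemia with pembrolizumab. The events may be few, but the instructions for them should not conflict.

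The conclusion rests on reading the note as written, without exemptions, and on the Section 7.1 meaning of life-threatening applying in Table 6.1. The hematologic conflict does not depend on that second assumption, since row and note share the same term. Nothing here implies which instruction is clinically right.

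**What to change.** Reconcile the Table 6.1 note with the hematologic, type 1 diabetes/hyperglycemia and hypothyroidism rows. This can be done by changing the note, by changing the rows, by listing the rows exempt from the note, or by stating which takes precedence. The result should give one instruction per event, covering both limbs of the note. State whether life-threatening in the note carries the Section 7.1 meaning, and align the opening sentence of Section 6.1 with the outcome. The sponsor's medical lead decides which instruction stands.

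The cost is wording in one table and one sentence, a short amendment and a memo to sites. The statistical section needs no change.
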